Research Protocol

Project Title

Peak cardiac output determined using inert gas rebreathing: A comparison of two exercise protocols

Principal Investigator

[name].
Professor
Department of Kinesiology
McMaster University

Student Investigator

[name], M.Sc.
Ph.D. Candidate
Department of Kinesiology
McMaster University

Background and rationale

The “gold standard” methods for determining cardiac output (Q) are the direct Fick and thermodilution techniques (1). Both are highly technical and very invasive, requiring arterial catheterization. Q can be estimated non-invasively using inert gas rebreathing (IGR). The IGR method involves taking 5-6 breaths from a closed-circuit rebreathing bag that contains a mixture of oxygen and inert gases. The Innocor (COSMED, Italy) is a popular commercially available device that uses oxygen (94%), an inert blood soluble gas (nitrous oxide, 5%), and an inert blood insoluble gas (sulfur hexafluoride, 1%) (2). Photoacoustic gas analyzers monitor the expired air and measure the disappearance rate of the blood soluble gas relative to the blood insoluble gas over the course of the rebreathing period to estimate Q.

IGR-derived Q using the Innocor correlates well with the direct Fick ($r=0.95$) and thermodilution ($r=0.94$) methods during maximal exercise (3, 4). A recent review comprising 10 clinical studies found that the correlation between IGR and the Fick method was higher than the correlation between the thermodilution and Fick method during submaximal steady state exercise (IGR vs Fick: $r=0.84$ [95% CI 0.74-0.90]; thermodilution vs Fick: $r=0.73$ [95% CI 0.61-0.82]), and that IGR demonstrated good Bland-Altman Limits of Agreement with the Fick method (1).

Moreover, IGR had a higher reliability than the thermodilution method (IGR typical error [TE]=7.2%; thermodilution TE=13.2%) (1). Further, the Fick and thermodilution methods yield greater inter-subject variability estimated by standard deviation during maximal exercise compared to IGR (Fick standard deviation [SD]=3.9 L/min; thermodilution SD=3.8 /min; IGR SD=2.2 L/min) (5). Therefore, IGR provides a noninvasive estimation of peak cardiac output (Q_{peak}) that is accurate and potentially more reliable than invasive measures. The latter may be

owing to the fact that the relative simplicity of the IGR method reduces assessor variability, and it is less susceptible to excessive movement during exercise.

A challenge inherent to the IGR technique for estimating Q_{peak} is the selection of an appropriate exercise protocol and deciding when to initiate the rebreathing procedure. The rebreathing requires a measurement period of ~ 10 s during “maximal” exercise or as close to this point as possible, while ensuring the participant can maintain the exercise load throughout the entire rebreathing period. There is no consensus regarding the optimal exercise protocol to measure IGR-derived Q_{peak} . One commonly-used protocol involves an incremental (step) exercise test with rebreathing initiated when the participant reaches a heart rate (HR) that is within 5 bpm of a previously determined peak value (the Q_{step} protocol) (6). Iterations of this protocol involve initiating rebreathing when the participant self-reports that they are ~ 30 s from exhaustion, or when the workload corresponds to the peak power output from a previously completed step test to exhaustion (7), as opposed to when a pre-determined HR is reached. The TE of step test determinations of Q_{peak} have been reported to be $\sim 7\%$ (1, 8).

We recently developed an exercise protocol for the IGR-derived estimation of Q_{peak} (the Q_{CL} protocol) (9) that was modelled after tests of $VO_{2\text{peak}}$ that involve a “verification phase” (10, 11). It involved a ramp exercise test to elicit $VO_{2\text{peak}}$, followed by a constant load exercise phase after a brief recovery interval, and the TE was 4.7% (9). The constant load phase was performed at $\sim 90\%$ of the workload that elicited $VO_{2\text{peak}}$, with rebreathing to estimate Q_{peak} initiated after 2 minutes. This protocol was developed based on previous research studies that found that constant load exercise performed at $>85\%$ W_{peak} can elicit comparable VO_2 values, and HR values that are within $\sim 5\%$ of those obtained at the end of a ramp $VO_{2\text{peak}}$ test (9–12). The use of a constant load phase to measure Q_{peak} allows for the measurement of this parameter during the same test as used

to determine $VO_{2\text{peak}}$, in contrast to the Q_{step} protocol which must be performed on a different day. This may be convenient for training studies (i.e., reducing the need for two tests). No study has compared Q_{peak} between the Q_{CL} and Q_{step} protocols, and no study has assessed the reliability of the Q_{CL} and Q_{step} protocols for determining Q_{peak} within the same group of participants.

Objectives

Primary objective

To test whether the Q_{peak} produced from the Q_{CL} protocol is not meaningfully different from the Q_{step} protocol using a non-inferiority design.

Secondary objectives

(1) to determine the reliability of the Q_{CL} and Q_{step} protocols, (2) to determine whether the VO_2 and HR obtained from the two experimental protocols are not different from the $VO_{2\text{peak}}$ and HR_{peak} obtained from the baseline $VO_{2\text{peak}}$ test, and (3) to determine whether the VO_2 measured by the Innocor is lower than the metabolic cart.

Hypothesis

We hypothesize that the Q_{CL} protocol will produce a Q_{peak} that is not different (by a margin of noninferiority of 0.5 L/min) compared to the Q_{step} protocol. A Q_{peak} of 0.5 L/min was the TE in a previous study in our laboratory (9), and is therefore deemed to be the minimum meaningful difference for determinations of Q_{peak} .

Methods

Participants

Participants will be recruited from the McMaster community and surrounding area through printed posters, web-based advertisements, and word of mouth.

Inclusion criteria:

- Adults aged 18-35 years.
- Meeting the Canadian 24-hour Movement Guidelines for Adults for aerobic physical activity, i.e. ≥ 150 minutes of moderate to vigorous activity per week (13). This will be assessed using the Canadian Society for Exercise Physiology Get Active Questionnaire (GAQ) (14).

Exclusion criteria:

- Diagnosis of any cardiovascular, respiratory, or metabolic disease that would preclude participation from a clinical standpoint, as determined by answering ‘yes’ to any of the questions on the first page of the GAQ.

Details of the experimental protocol, purpose and potential risks of participation will be explained to all participants and written informed consent will be obtained prior to participation in the study. This study has been approved by the Hamilton Integrated Research Ethics Board (Project # 13339).

Sample size determination

A calculation performed using G*Power (v 3.1.9.2) for a two-tailed dependent means (matched pairs) t-test estimated that a sample size of 34 was required to detect a medium effect size ($d_z=0.5$) with 80% power at an alpha level of 0.05 (Figure 1). A medium effect size was deemed

reasonable based on determinations made in G*Power using our hypothesized minimum meaningful difference (0.5 L/min) and typical means, standard deviations and correlations determined in our laboratory and reported in the literature for Q_{peak} (5, 9, 15).

[figure not shown]

Figure 1: G*Power sample size output.

Experimental procedures

This study will use a randomized within-subject crossover design. All data collection will take place in the Human Performance Laboratory at McMaster University in Hamilton, Ontario, Canada. Following preliminary screening and recruitment into the study, participants will attend the laboratory on 9 separate occasions, each separated by ≥ 48 hours (Figure 2). The first visit will involve the determination of $VO_{2\text{peak}}$ (Quark CPET metabolic cart, COSMED, Italy), HR_{peak} (Polar A3, Finland), and W_{peak} (Lode Excalibur Sport V2.0, Groningen, The Netherlands). On the second visit, participants will be familiarized with the inert gas rebreathing procedure and measurement of Q will be performed at rest and during a brief exercise test consisting of a 3-minute warm up at 50 W followed by an immediate increase to 80% of peak workload (W_{peak}) with rebreathing initiated after 2 minutes at 80% W_{peak} . The third visit will involve a verification test with the same measures as the first test. The highest values for $VO_{2\text{peak}}$, HR_{peak} and W_{peak} will be used to determine appropriate parameters and for comparative purposes with the subsequent main experimental trials. There will then be a 1-week break before beginning the experimental trials to reduce the likelihood of a testing-induced training effect. The experimental trials will consist of 6 different visits to the laboratory using a randomized repeated measures design (Experimental trials, Figure 2). Participants will perform the Q_{CL} protocol on 2 separate occasions and the Q_{step} protocol on 2 separate occasions. Q_{peak} (Innocor, COSMED, Italy) and HR_{peak} (Polar) will be assessed during each of these visits. On an additional 2 visits, participants will perform the Q_{CL} (one visit) and Q_{step} protocols (one visit) with VO_2 measured in place of Q_{peak} using the same metabolic cart as the one used for the baseline $VO_{2\text{peak}}$ test (Quark CPET metabolic cart, COSMED, Italy). These tests are referred to as $VO_{2\text{CL}}$ and $VO_{2\text{step}}$ in Figure 2. All 6 experimental trials will be randomized for each participant. The first Q_{CL} and the first Q_{step}

test will be used to compare Q_{peak} *between* protocols, and the values obtained from the first vs the second Q_{CL} and Q_{step} tests will be used to determine the TE *within* each protocol. The VO_{2peak} from the VO_{2CL} and VO_{2step} protocols will be compared to the VO_{2peak} from the baseline VO_{2peak} test.

Participants will be instructed to maintain their habitual diet between testing sessions and abstain from strenuous exercise and alcohol consumption for a minimum of 24 hours before testing. A 24-hour dietary log will be completed before every experimental trial testing session.

Participants will be instructed to arrive to the laboratory hydrated. Testing sessions will take place at the same time of day ± 1 hour for each participant. All exercise protocols will use a cycle ergometer (Lode Excalibur Sport V2.0, Groningen, The Netherlands).

[figure not shown]

Figure 2: Schematic of study design. Q fam., cardiac output familiarization; Verif, Verification; h, hours. Each set of 2 experimental trials will be performed in random order.

Randomization

The order of the 6 experimental trials will be determined using simple randomization in Microsoft Excel. For each participant, a random, 15 decimal place number between 0 and 1 will be assigned to each experimental trial using the “=rand()” formula. The experimental trials will

be sorted using the “sort largest to smallest” function to determine the order in which the trials will be performed. The random sequence generation will be performed by a study investigator who is not involved in participant enrollment and will inform the other investigators of the order of experimental trials for each participant 24 hours before their first session. Due to the nature of the experiments, we are unable to blind the participants or researchers to the order of experimental tests; however, we will limit performance bias by blinding participants to the study hypotheses.

Primary outcome measure

Q_{peak} determined using the first Q_{CL} and Q_{step} protocols.

Secondary outcome measures

Reproducibility of Q_{peak} for each of the two IGR protocols based on the 1st and 2nd experimental trial for each test.

HR_{peak} determined during to the two IGR protocols.

$VO_{2\text{peak}}$, HR_{peak} , and W_{peak} determined during the baseline and verification $VO_{2\text{peak}}$ tests.

$VO_{2\text{peak}}$ between the $VO_{2\text{peak}}$ test, the $VO_{2\text{CL}}$ protocol and the $VO_{2\text{step}}$ protocol.

$VO_{2\text{peak}}$ between the Q_{CL} vs $VO_{2\text{CL}}$ tests and the Q_{step} vs $VO_{2\text{step}}$ tests.

$VO_{2\text{peak}}$ tests

For the determination of $VO_{2\text{peak}}$, participants will perform a progressive exercise test to maximal voluntary exertion using an electromagnetically braked cycle ergometer (Lode Excalibur Sport V2.0, Groningen, The Netherlands). Following a 3 min warm-up at a fixed workload of 50 W, a ramp protocol will be applied with a linear workload increase of 1 W every 2 s (30 W/min). The

precise protocol will be standardized for a given participant and intend to achieve a ramp duration of ~10 min (range: 5-15 min). Pedaling cadence will be chosen by the participant and will be required to be ≥ 60 rpm. A 3-min recovery phase will be performed at 50 W. Gas exchange and ventilatory variables will be continuously determined using a metabolic cart (Quark CPET metabolic cart, COSMED, Italy). Data will be averaged over 10-s intervals and $VO_{2\text{peak}}$ will be defined as the highest 30-s average over three consecutive intervals. Heart rate will be recorded continuously (Polar A3, Finland) and HR_{peak} will be defined as the highest 2-s average. Data-based cutoffs for age-stratified secondary exhaustion criteria based on peak respiratory exchange ratio and age-predicted maximal heart rate (16) will be used to verify that the test involved maximal effort. The highest $VO_{2\text{peak}}$, HR_{peak} , and W_{peak} between the baseline and verification tests will be regarded as the ‘true’ peak.

Q_{CL} protocol

This protocol involves a ramp exercise test to exhaustion, followed by a constant work rate test that is initiated after 10 minutes of active recovery (Figure 3). The ramp phase uses the same protocol as the $VO_{2\text{peak}}$ test (described above). The constant work rate phase will begin with a 1-minute warmup at 50 W. The warmup will be followed by an immediate increase to an intensity equivalent to 90% of the W_{peak} elicited during the baseline ramp $VO_{2\text{peak}}$ test (90% W_{peak}). HR (Polar A3, Finland) and VO_2 (Innocor, COSMED, Italy) will be monitored continuously throughout the test. The rebreathing procedure to measure Q_{peak} (Innocor, COSMED, Italy) will be initiated after 2 minutes of cycling at 90% W_{peak} .

[figure not shown]

Figure 3: Q_{CL} protocol.

Q_{step} protocol

This test is modelled after an incremental exercise protocol that has commonly been used to assess Q_{peak} (6, 15, 17) including to assess potential changes in Q_{peak} after an exercise intervention (15). The test will begin with a 3-minute warm-up at 50 W and workload will subsequently be increased by 30 W every 1 minute (Figure 4). HR (Polar A3, Finland) and VO_2 (Innocor, COSMED, Italy) will be monitored continuously throughout the test. The rebreathing procedure to measure Q_{peak} (Innocor, COSMED, Italy) will be initiated when the participant reaches a HR that is within 5 bpm of their previously determined HR_{peak} obtained from baseline VO_{2peak} testing (visit #1 or 3 from Figure 2). W_{peak} will be calculated as $W_{peak} = W_{completed} + 30 \times (t/60)$ where $W_{completed}$ is the last completed workload and t is the time in s maintained during the final workload.

[figure not shown]

Figure 4: Q_{step} protocol.

VO_{2CL} protocol

The VO_{2CL} protocol will be identical to the Q_{CL} protocol (Figure 3), except VO_2 will be monitored continuously using the same metabolic cart as the $VO_{2\text{peak}}$ test (Quark CPET metabolic cart, COSMED, Italy), and Q_{peak} will not be assessed. The constant load $90\% W_{\text{peak}}$ phase will be 2 min and 15 s in duration; the final 15 s is added to account for the approximate time it would take for the IGR to occur.

VO_{2step} protocol

The VO_{2step} protocol will be identical to the Q_{step} protocol (Figure 4), except VO₂ will be monitored continuously using the same metabolic cart as the VO_{2peak} test (Quark CPET metabolic cart, COSMED, Italy), and Q_{peak} will not be assessed. Participants will continue cycling for an additional 15 s after reaching a HR that is within 5 bpm of HR_{peak} to account for the approximate time it would take for the IGR to occur.

Statistical analysis

A two-tailed paired samples t-test will be performed to compare each of Q_{peak}, HR_{peak}, and W_{peak} between the two experimental conditions (Q_{CL} vs Q_{step}). A two-tailed paired samples t-test will be performed to compare each of VO_{2peak}, HR_{peak}, and W_{peak} between the baseline and verification VO_{2peak} tests, to compare Q_{peak} between the first and second Q_{CL} and Q_{step} tests, and to compare VO_{2peak} between the VO_{2peak} test and each of VO_{2CL} and VO_{2step}. Significance will be set to p<0.05. Effect sizes will be reported as Cohen's d_z and 95% confidence intervals (CI) will also be determined. Q_{peak} estimated by the Q_{CL} protocol will be considered noninferior to the Q_{step} protocol if the 95% CIs for the change in Q_{peak} fall within the margin of noninferiority (i.e., 0.5 L/min) (18, 19).

Reliability of each experimental protocol and of the VO_{2peak} tests will be calculated as the TE using the following formula (20):

$$TE = (SD_{diff} \div \sqrt{2} \div grand\ mean) \times 100$$

Where SD_{diff} is the standard deviation of the difference scores between the 2 measurements, and the grand mean is the mean of all measurements included in the analysis. The TE will be expressed as a percentage.

Perspectives and significance

IGR provides a noninvasive method for determining Q_{peak} , and assessing potential changes elicited by acute and chronic exercise interventions. The proposed work will systematically compare two methods for determining IGR-derived Q_{peak} , to assess potential differences between protocols as well as reliability of each method. This research will provide novel comparative data and inform decisions by researchers regarding choice of Q_{peak} protocol in future studies.

Strategies to reduce bias

Selection bias

The order of experimental trials will be randomized for each participant using Microsoft Excel by an investigator not involved in participant enrollment. This investigator will inform the other investigators of the trial order after baseline testing, and 24 hours before the first experimental trial for each participant. The investigator performing the randomization will play a secondary role in data collection.

Performance and detection bias

Given the distinct nature of each experiment, it is not possible to blind investigators or participants to the order of experimental trials. However, we will limit performance bias by blinding participants to the study hypotheses.

Reporting bias

The current protocol, which clearly states the primary and secondary outcomes and hypotheses, will be published in an open access repository prior to participant recruitment.

Summary of analysis plan

| Question | Hypothesis | Data collection plan | Analysis plan | Interpretation |
|---|--|---|--|--|
| Is Q_{peak} determined by Q_{CL} noninferior to Q_{step} ? | Q_{CL} is noninferior to Q_{step} . | Measure Q_{peak} following Q_{CL} and Q_{step} using a randomized within-subject design. | Calculate 95% CIs for the mean difference in Q_{peak} between Q_{CL} and Q_{step} . | Q_{CL} is noninferior to Q_{step} if the lower bound of the CI is within 0.5 L/min. |
| What is the reproducibility of the Q_{CL} and Q_{step} protocols? | Reproducibility will be similar between Q_{CL} and Q_{step} . | Measure Q_{peak} during 2 Q_{CL} tests and 2 Q_{step} tests in a randomized order. | Calculate the TE between 1) the 2 Q_{CL} tests, and 2) the 2 Q_{step} tests. | Result will provide an indication of Q_{peak} reproducibility. |
| Is the HR_{peak} different between Q_{CL} and Q_{step} ? | HR_{peak} will not be significantly different between Q_{CL} and Q_{step} . | Measure HR_{peak} during Q_{CL} and Q_{step} using a randomized within-subject design. | Perform a paired t-test for HR_{peak} between Q_{CL} and Q_{step} . | If HR_{peak} is not significantly different between Q_{CL} and Q_{step} , it suggests participants are similarly close to “max” values during both protocols. |
| What is the reproducibility of the $VO_{2\text{peak}}$ test? | The reproducibility for the $VO_{2\text{peak}}$ tests will be approximately 5%. | Measure $VO_{2\text{peak}}$ during the baseline and verification $VO_{2\text{peak}}$ tests. | Calculate the TE of the baseline and verification $VO_{2\text{peak}}$ tests. | Result will provide an indication of $VO_{2\text{peak}}$ test reproducibility. |
| Is the $VO_{2\text{peak}}$ measured from the Innocor noninferior to the Quark metabolic cart? | $VO_{2\text{peak}}$ from the Innocor will be inferior to the Quark metabolic cart. | Measure $VO_{2\text{peak}}$ during identical tests using the Innocor and the Quark metabolic cart (i.e., Q_{CL} vs $VO_{2\text{CL}}$ and Q_{step} vs $VO_{2\text{step}}$). | Calculate 95% CIs for the mean difference in $VO_{2\text{peak}}$ between Q_{CL} vs $VO_{2\text{CL}}$ and Q_{step} vs $VO_{2\text{step}}$. | Q_{CL} is noninferior to $VO_{2\text{CL}}$, and Q_{step} is noninferior to $VO_{2\text{step}}$ if the lower bound of the CI is within a margin of |

| | | | | |
|---|--|--|--|--|
| | | | | noninferiority of 0.2 L/min. |
| Do the experimental tests elicit VO_{2peak} that is noninferior to the VO_{2peak} test? | VO_{2peak} during the experimental tests will be noninferior to the VO_{2peak} test. | Measure VO_{2peak} during the VO_{2CL} , VO_{2step} , and baseline VO_{2peak} tests. | Calculate 95% CIs for the mean difference in VO_{2peak} between VO_{2CL} vs the baseline VO_{2peak} test and VO_{2step} vs the baseline VO_{2peak} test. | VO_{2CL} and VO_{2step} are noninferior to the baseline VO_{2peak} test if the lower bound of their respective CIs are within a margin of noninferiority of 0.2 L/min. |

Acknowledgments

We thank our colleagues who have provided input on the development of this proposal including those whose substantive contributions will be recognized with authorship on the resulting manuscript.

References

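### The stated 80% power is for a test of difference; under the plan's two primary decision rules, 34 participants give 62% or 81%, so the rule must be fixed and its power stated

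*Protocol*

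**What the plan says.** In the Protocol, Sample size determination says that a "two-tailed dependent means (matched pairs) t-test estimated that a sample size of 34 was required to detect a medium effect size". The settings are given as "required to detect a medium effect size ($d_z=0.5$) with 80% power at an alpha level of 0.05". The effect size is called "reasonable based on determinations made in G*Power using our hypothesized minimum meaningful difference (0.5 L/min) and typical means, standard deviations and correlations" from the laboratory and the literature. The text gives no SD of the paired differences and no expected true difference. The G*Power output (Figure 1) is not visible in the copy reviewed.

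The Objectives set a non-inferiority design, with the aim of showing no meaningful difference. The Hypothesis is that Q_CL gives a peak cardiac output "not different (by a margin of noninferiority of 0.5 L/min) compared to the Q_{step} protocol".

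The decision rule appears twice:

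- Statistical analysis: Q_CL is noninferior "if the 95% CIs for the change in Q_{peak} fall within the margin of noninferiority (i.e., 0.5 L/min").
- Summary of analysis plan, first row: Q_CL is noninferior when the lower bound of the interval is within 0.5 L/min. The upper bound is not mentioned.

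**The concern.** The calculation gives the chance of rejecting zero difference when the true difference is 0.5 SD. The primary conclusion runs the other way: it needs an interval narrow enough, and centred closely enough on zero, to exclude a difference of 0.5 L/min. The calculation places the true difference at 0.5 L/min, which is the margin itself, whereas the hypothesis is that there is no difference. No power is stated for the interval rule that decides the primary question, and because that rule is written in two ways, no single figure could be.

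At stake is how a failed result is read. If the interval does not meet the rule, readers will assume that a study with 80% power missed its aim. Under the both-bounds rule with truly identical protocols, about 38% of such studies would fail (100% − 62%).

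**Working it through.** **Inputs.** n = 34, d_z = 0.5, two-sided alpha 0.05 and 80% power (Sample size determination); margin 0.5 L/min (Hypothesis). The SD of differences is not stated; taking 0.5 L/min as d_z = 0.5 implies 0.5 / 0.5 = 1.0 L/min. A true difference of 0 is assumed from the hypothesis. No dropout allowance is stated, so 34 is taken as the number analysed.

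**1. The plan's own figure.** Paired t-test, noncentral t, df = n − 1, noncentrality d_z × √n = 0.5 × √34 = 2.92. Power is 79.5% at n = 33 and 80.8% at n = 34. The stated 34 reproduces.

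**2. Lower-bound rule (Summary of analysis plan).** Success means lower 95% bound > −0.5, a one-sided 0.025 test with noncentrality (0.5 + δ) / (SD / √n), where δ is the true Q_CL − Q_step difference. At δ = 0 and SD 1.0 this is again 2.92, so power is 80.8%. It matches the plan's figure because the margin was entered as the detectable difference and a two-sided 0.05 test has the same critical value as a one-sided 0.025 test.

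**3. Both-bounds rule (Statistical analysis, read literally).** Success means that both 95% bounds lie inside ±0.5. At δ = 0 each bound fails with probability 1 − 0.808 = 0.192, and the two failures almost never coincide, so power ≈ 1 − 2 × 0.192 = 0.616. Exact integration over the sample variance gives 61.6%, and 300,000 simulated trials give 61.7%. Reaching 80% needs n = 44.

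**4. If Q_CL is truly lower (SD 1.0, n = 34).**

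| True difference (L/min) | Lower bound only | Both bounds |
|---|---|---|
| 0 | 80.8% | 61.6% |
| −0.1 | 62.0% | 54.4% |
| −0.2 | 39.7% | 37.4% |

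**5. If the SD of differences is not 1.0 (true difference 0, n = 34).**

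| SD (L/min) | Lower bound only | Both bounds |
|---|---|---|
| 0.8 | 94.3% | 88.5% |
| 0.9 | 88.2% | 76.4% |
| 1.0 | 80.8% | 61.6% |
| 1.1 | 73.0% | 46.0% |
| 1.2 | 65.5% | 31.4% |

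**6. Is 1.0 L/min plausible on the plan's figures?** Background and rationale gives a typical error of 4.7% for Q_CL and about 7% for Q_step. With independent errors, measurement error alone gives an SD of differences of mean × √(0.047² + 0.07²) = 0.0843 × mean. The prior laboratory study supplies both 0.5 L/min and 4.7%, implying a mean of 0.5 / 0.047 = 10.6 L/min. The SD is then 0.0843 × 10.6 ≈ 0.90 L/min, with power 88% (lower bound) or 77% (both bounds). The SD would pass 1.0 L/min once the mean exceeds 1.0 / 0.0843 = 11.9 L/min.

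**The case against.** The best defence is that this is labelled a non-inferiority design throughout, that Statistical analysis also concludes only noninferiority, and that the summary table gives the operational rule as the lower bound alone. On that reading 34 participants give 80.8% at zero difference, the same as the stated power. This stands, and it limits the point. A reader might infer that the study simply has 62% power. The document does not support that, because 62% follows from only one of its two written rules. The defence does not remove the problem, however. The both-bounds wording is in the Statistical analysis section itself, and the aim of showing no meaningful difference fits it.

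A reader might also infer that an SD of 1.0 L/min contradicts the plan's typical errors. It does not: at the only mean the document implies, those errors give about 0.90 L/min, slightly favourable to the plan. The reference list describes that prior study's participants as previously untrained, while this trial recruits active adults, so a higher mean and a larger SD are possible. But no mean for this sample is given, so that remains an assumption.

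Finally, the unseen Figure 1 may list further inputs. It would not change the test named in the text or the two rules.

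**Conclusion.** The point holds in this form. The sample size is justified by a test of difference, while the primary conclusion rests on a confidence interval rule that the plan states in two incompatible ways. With the implied SD of 1.0 L/min, a true difference of 0 and 34 analysed, the stated 80% is right for the lower-bound rule (81%) and wrong for the both-bounds rule (62%). Even for the lower-bound rule it relies on zero true difference, which the sample size paragraph does not say.

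The arithmetic is firm. The SD and the true difference are inferred rather than stated, and the table by SD shows how strongly the answer depends on the first of these. The material does not show that 34 is too few: that depends on which rule governs.

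**What to change.** - Reconcile Statistical analysis with the first row of the Summary of analysis plan, so that one primary decision rule remains, stating whether one or both bounds must clear 0.5 L/min.
- Replace the G*Power statement with the power of that rule at n = 34: 81% for the lower bound or 62% for both bounds, at SD 1.0 L/min and true difference 0.
- State the assumed SD of differences (now implicitly 1.0 L/min), its source and the assumed true difference.
- Add a short sensitivity row for the SD, for example 0.8 to 1.2 L/min as above.

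Averaging the two replicate tests per protocol is not part of this fix. Experimental procedures and Primary outcome measure name the first test of each protocol as primary, so averaging would change the prespecified outcome.

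The cost is one rewritten paragraph and one aligned sentence, with no extra enrolment. The drawback is that the stated power may become less favourable, clearly so if the both-bounds rule is kept.

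### The VO2peak comparison in secondary objective 2 sets one experimental test against the higher of two baseline tests, so a truly equal protocol is expected to look lower

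*Protocol*

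**What the plan says.** Secondary objective 2 (Objectives) asks whether VO2 and HR "obtained from the two experimental protocols are not different from the" peak values of the baseline test.

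- **Comparator, by rule.** Experimental procedures says the highest VO2peak, HRpeak and Wpeak from visits 1 and 3 "will be used to determine appropriate parameters and for comparative purposes with the subsequent main experimental trials". The VO2peak tests section repeats that the highest value "between the baseline and verification tests will be regarded as the ‘true’ peak".
- **Comparator, by name.** Experimental procedures also says that the values from the VO2CL and VO2step "protocols will be compared to the VO_{2peak} from the baseline VO_{2peak} test". Objectives and the Summary of analysis plan likewise name a single baseline test.
- **Experimental side.** "On an additional 2 visits, participants will perform the" two protocols with the metabolic cart, one visit each. There is therefore one VO2CL and one VO2step value per participant.
- **Analysis.** Statistical analysis plans two-tailed paired t-tests of VO2peak between the VO2peak test and each of VO2CL and VO2step at p<0.05. The Summary of analysis plan declares noninferiority "if the lower bound of their respective CIs are within a margin of noninferiority of 0.2 L/min".

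**The concern.** The two sides of the comparison are not built alike. Each experimental value is one draw; the reference is the better of two. Random variation between visits pushes a maximum upwards and leaves a single value where it is, so the expected difference is negative even when the protocols elicit exactly the same VO2peak. Nothing in the protocol allows for this. More participants would not help: the shortfall stays the same size while the confidence interval narrows around it.

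At stake is the answer to the VO2peak part of objective 2. The t-test could report a difference produced by the choice of comparator, and the noninferiority reading gives up part of its margin before any real difference is counted.

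**Working it through.** **Inputs from the protocol.** n = 34, two-sided alpha 0.05 (Sample size determination); margin 0.2 L/min and hypothesised VO2peak TE of about 5% (Summary of analysis plan); TE = SD of the differences / √2 / grand mean (Statistical analysis), which is the within-person SD, s, as a fraction of the mean.

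**Assumptions.** The protocol gives no mean VO2peak, so 2.5-4.0 L/min is used. Errors are taken as normal, independent and of equal size across tests, with no learning effect between visits.

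**Check of the stated sample size.** The exact noncentral-t calculation for a two-sided paired t-test with d_z = 0.5 gives n = 34 with power 0.808, as the protocol states.

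**Step 1: size of the shortfall.** For two exchangeable tests, E[max] − mean = s/√π = 0.564 s. At TE 5% this is 0.564 × 5% = 2.8% of VO2peak.

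| Assumed mean (L/min) | Shortfall (L/min) | Share of 0.2 margin |
|---|---|---|
| 2.5 | 0.071 | 35% |
| 3.0 | 0.085 | 42% |
| 3.5 | 0.099 | 49% |
| 4.0 | 0.113 | 56% |

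**Step 2: the t-test.** The variance of (single − maximum) is s² + s²(1 − 1/π), so its SD is s√(2 − 1/π) = 1.297 s. The standardised shortfall is 0.564/1.297 = 0.435. Because s cancels, this holds at any TE and any mean. With n = 34 the noncentrality is 0.435 × √34 = 2.54, and the noncentral t gives a rejection rate of 0.692. Simulation (20,000 trials per setting) gave 0.688-0.696, with every rejection in the direction of the experimental test being lower. With the first test alone or the mean of two as comparator, the rate was about 5%.

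**Step 3: noninferiority.** Simulated chance that the lower 95% limit lies above −0.2 L/min, under true equality:

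| TE | Comparator | 2.5 | 3.0 | 3.5 | 4.0 L/min |
|---|---|---|---|---|---|
| 2% | highest of two | 100% | 100% | 100% | 100% |
| 3% | highest of two | 100% | 100% | 100% | 99.8% |
| 4% | highest of two | 100% | 99.7% | 96.4% | 84.7% |
| 5% | highest of two | 99.5% | 91.7% | 71.0% | 47.1% |
| 5% | first test only | 100% | 99.9% | 99.6% | 98.0% |
| 5% | mean of two | 100% | 100% | 100% | 99.7% |

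**Step 4: precision of the alternatives.** The variance of the difference is 2s² against a single test and 1.5s² against the mean of two, so averaging removes the bias and is also more precise than one test.

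**The case against.** **The comparator may not be the maximum.** If the baseline VO2peak test means visit 1 alone, the bias vanishes. Statistical analysis separates the baseline test from the verification test, which supports that reading. Against it, Experimental procedures states the comparative use of the highest value outright, and the Q_step section describes baseline testing as visit 1 or 3. The figures above are therefore conditional. A reader might infer a flat contradiction between sections; the wording can be read consistently, with the baseline covering both visits, but it is not settled.

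**Noninferiority is the deciding analysis.** The Summary of analysis plan answers this question by confidence interval and margin and gives no rule for interpreting the t-test here. A small significant difference would not overturn noninferiority. That stands, and it makes the 69% less decisive. The t-test is nevertheless planned, and objective 2 is worded as no difference.

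**The bias is conservative.** It makes noninferiority harder to show and, under these assumptions, does not favour a false claim. This also stands.

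**The best of two is a sensible peak.** If one test fell short through effort, averaging would lower the benchmark. That is a fair reason to keep the maximum for setting parameters. It does not justify the asymmetry, because an off day on VO2CL or VO2step has no second attempt to replace it.

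**Heart rate.** A reader might extend the point to HR, which objective 2 names. The documents do not support that. HRpeak is assessed at both visits of each Q protocol, and neither Statistical analysis nor the Summary plans a test of experimental HR against baseline HRpeak. The step tests also tie HR to within 5 bpm of HRpeak by design.

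**Conclusion.** The point holds for the VO2peak part of secondary objective 2, provided the comparator is the highest of two tests, as Experimental procedures and the VO2peak tests section say. The built-in shortfall is 0.564 × TE. Its effect on the t-test is large at any TE; its effect on noninferiority depends on TE and mean VO2peak, from almost none at TE 2-3% to serious at TE 5% with a mean of 3.5 L/min or more. The 5% is the protocol's hypothesis and the means are assumed, so it cannot be inferred that noninferiority would probably fail.

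Nor does the point reach further: the primary comparison of the first Q_CL with the first Q_step, the reliability analyses and the sample size of 34 are unaffected.

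**What to change.** Name one VO2peak comparator in advance for VO2CL and VO2step: preferably the mean of the baseline and verification tests, or else one specified test. Use the same wording in Objectives, Experimental procedures, VO2peak tests, Statistical analysis and the Summary of analysis plan. Keep the highest value for setting test parameters, and report the comparison against it as a sensitivity analysis, noting its upward bias.

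The cost is wording only, since both baseline tests are already planned. The small downside is that a submaximal baseline test would lower the mean; the planned exhaustion criteria and the sensitivity analysis address this.
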